Efficacy of intraoperative CT feedback of wedge resected lung for the assessment of surgical margin

Protocol Version #2

Date: 26APR2024

Research Objectives

Aim1: To assess how surgical outcomes are impacted by intraoperative CT feedback.

Aim2: To assess the validity of the additional resections.

Study Background

Lung cancer is the most prevalent cancer and the leading cause of cancer death in Canada. In 2020, lung cancer resulted in the deaths of 21,200 Canadians (1). The high mortality reflects both its high incidence and low survival. Although it is one of the most aggressive malignant tumors, as with many other types of cancer, patients can live cancer-free if the diagnosis is accurate and timely treatment is administered. Low-dose computed tomography (LDCT) scans can help find abnormal areas in the lungs that may be cancerous. Research has shown that scanning patients at higher risk of lung cancer using LDCT saved more lives compared to chest x-rays (2). In Canada, opportunistic screening is occurring in at least six provinces and implementation of organized programs is expected in the coming years (3). The increased prevalence of CT screening and advances in diagnostic technology, particularly the widespread use of thin-slice computed tomography, have enabled increased detection of early-stage small lung cancers (4). Early-stage lung cancer is often featured as a ground-glass opacity (GGO) associated with a pathological lepidic growth pattern that is considered to be related to a more favorable prognosis (5). Therefore, these GGO-dominant lung cancers could be optimal candidates for sublobar resections, which is to remove a section of a lobe of the lung that contains the lung cancer and a margin of healthy tissue around the cancer. This is an alternative to the conventional, more radical, pulmonary lobectomy (6, 7). Sublobar resection, including segmentectomy and wedge resection, is less invasive, sparing more healthy lung tissue and is associated with improved patient recovery. However, an increasing number of hazy lung tumors are also being detected, which are difficult to localize intra-operatively as they are

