CT margin was calculated as follows: i) resected lung specimen was inflated with 25-gauge needle and an appropriately syringe, while monitoring to prevent alveolar wall destruction using a pressure transducer. ii) The specimen was placed on a CT scanner with adjustment of staple line perpendicular to CT axial line and scanned CT in Spatio-temporal targeting and amplification of radiation response (STTAAR) innovation center. iii) CT margin was defined as the distance between tumor and tumor side of the staple line, and measured. After the assessment, the specimen was delivered to the surgical pathology department, and standard pathological examination was performed.

2) Results

54 patients were enrolled. In this study. In 4 patients (7.4%), poorly inflated specimen caused the tumor to be undetectable, which we subsequently excluded. Consequently, 92.6% of cases, 50 patients (52 specimens) were analyzed. Surgical margin measured by CT was significantly longer than pathological margin (11.74 ± 8.52 VS 10.08 ± 7.22 , $p = 0.033$). 21% surgical margin length reduction was observed from CT to pathological assessment. Medial correlation was found between CT assessed margin and pathological margin ($r = 0.7679$). Margin assessment for resected lung is feasible and accessible way to identify tumor and surgical margin during surgery. Surgeons should be aware that CT assessed surgical margin will be longer than pathological margin.

Sample size

We aim to evaluate 80 cases over 2 years. We would like to include all 9 thoracic surgeons in our division to evaluate the impact to the surgical outcome “surgical margin” over the course of the study. As this is unlikely as not all surgeons will perform wedge resections, we will enroll consecutive patients regardless of who the attending surgeon is.

Patient Groups

Inclusion criteria:

- Patients scheduled for lung wedge resection for primary lung cancer or metastatic lung tumor (included suspected lesions).

- 18 years of age or older.

Exclusion criteria:

- Any patients with inability to give informed consent
- Wedge resection for non-therapeutic purpose, e.g. diagnostic purpose.

Study Plan and Methods

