This is a single center clinical trial. We will ask thoracic surgeons in our institution to work together for this research. A total of 80 patients scheduled for wedge resections for lung malignancies (including suspected patients) will be enrolled in this study. The attending surgeon will introduce the study to the patients and a research coordinator will then go through the consenting process, answer any questions and enroll the patient if they wish to participate within one month before surgery.

We will enroll 80 patients in 2 years for this study. Prior to first surgery, every surgeon will be asked to complete a questionnaire 1 to investigate the background of surgeon. At each surgery, we ask for questionnaire 2 orally before and after resection to assess the contribution of feedback to margin results. Once the wedge resection is performed, the resected specimen will be brought to 7th floor in STTARR innovation center in Princess Margaret Cancer Research Tower (PMCRT). Resected lung specimen will be inflated with 25-gauge needle and appropriately sized syringe. The air injection pressure as well as the total inflation pressure will be continuously monitored to prevent alveolar wall destruction using a pressure transducer. For the precise surgical margin measurement, the staple line is adjusted perpendicular to CT axial line. Surgical margin will be measured and its image will be captured. Surgical margin is defined as the distance from tumor to the tumor side of staple line (not including the width of staple line). The data (included CT image and CT surgical margin) will be numbered and exclude individual information (only include study number and date). The data will be transferred from CT scan to our laptop using universal serial bus (USB), then shared with surgeons by tablet in operating room through online storage service

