such as OneDrive or directly with laptop or USB. These processes are expected to take about up to 20 minutes. Surgeons will wait and refer to these results, and make a decision if additional resection should be made. The lung specimen will be delivered to the pathological laboratory and routine pathologic work up will be proceeded per standard care, including fixation, gross assessment, and selection of clinically relevant tissue blocks for sectioning, staining, and microscopic assessment. Within several days after surgery, we will send the CT measured margin length and reconstructed 3D image of the resected specimen to the attending surgeon, and ask them to complete the rest of questionnaire 2. This is to evaluate the usefulness of the CT image feedback and the surgeon's satisfaction for each case.

Additionally, once the pathological result for each patient is revealed, surgeons will receive the results of the margin length comparison (CT based margin and pathological margin). After the total course of surgery, we will ask each surgeon individually for questionnaire 3 after feedback of the individual result of this study to assess the satisfaction by intraoperative feedback.

Benefits

Intraoperative feedback of surgical margin measured by CT correlates to pathological margin length, and could help make a decision for additional resection. Patients with a confirmed sufficient margin could have better local cancer control.

Risks

Additional resection could induce complication such as air leakage.

Extra time commitment for patients

The entire intraoperative feedback process takes about up to 20 minutes, further increasing the operation time.

Outcome Measures

The primary outcome of the study will include (1) the contribution of intraoperative feedback to treatment decision, and its validity, and (2) assessing how intraoperative feedback affects surgical margins over the course. The secondary outcome will be the assessment of surgeons' satisfaction with intraoperative

feedback.

Statistics

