A linear mixed model will be performed to analyze the difference of the process between expected and actual margin over the course. Pearson's correlation analysis will be performed to analyze the correlation between the parameters measured on CT and on pathological analysis. Limits of agreement analysis will be performed per the Bland-Altman method to evaluate agreement between preoperative expectation for surgical margin and actual margin. ROC curves will be used to assess the CT margin to predict short pathological margin. GraphPad Prism8 (GraphPad Software, La Jolla, CA, USA) and R (for linear mixed model) will be used for statistical analysis. All p-values will be based on a two-sided hypothesis, with p-values < 0.05 indicating statistical significance.

Data Collection and Monitoring

The following data will be collected prospectively using source documents and a database specially constructed for the purpose. Data will be collected prospectively on all patients. Due to the low risk and influence for the patients involved in this study, a DSMB is not required.

- (1) Patients' background (age, gender, body weight, body mass index, history, smoking habit, preoperative diagnosis)
- (2) Preoperative CT information (tumor location, tumor size, CT appearance, Consolidation tumor ratio, distance between tumor and pleura)
- (3) Surgical information (surgery date, attending surgeon's study number, operative procedure, operative duration, preoperative marking, intraoperative CT image acquisition time, tumor size in intraoperative CT, margin length in intraoperative CT, additional resection, procedure change, intraoperative findings)
- (4) Pathological results (pathological diagnosis, tumor size, tumor spread through air space, pathological margin length)
- (5) Others (postoperative complication, length of stay)
- (6) Questionnaire results including surgeons' study number (see questionnaire section)

Access to Source Data/Documents

Access to the study data will be permitted for study investigators, coordinators,

and UHN REB.

Consent

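### Primary outcome 2 concerns surgical margins over the course, but the only analysis over time targets the expected-versus-actual difference and does not name the actual-margin trend as the result

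*Protocol*

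**What the plan says.** Aim 1 under Research Objectives is "To assess how surgical outcomes are impacted by intraoperative CT feedback". Sample size says all nine surgeons are wanted in order to "evaluate the impact to the surgical outcome", which it names as the surgical margin over the course of the study. Outcome Measures makes "assessing how intraoperative feedback affects surgical margins over the course" the second primary outcome.

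Study Plan and Methods defines the measurement: "Surgical margin is defined as the distance from tumor to the tumor side of staple line", taken on CT of the resected specimen. It also explains the questionnaire: "At each surgery, we ask for questionnaire 2 orally before and after resection to assess the contribution of feedback to margin results".

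Statistics lists four analyses:
- the linear mixed model: "A linear mixed model will be performed to analyze the difference of the process between expected and actual margin over the course";
- Bland-Altman limits of agreement, to "evaluate agreement between preoperative expectation for surgical margin and actual margin";
- Pearson correlation of CT with pathological measurements;
- ROC curves for CT margin as a predictor of a short pathological margin.

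Only the mixed model has a time element.

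**The concern.** Three sections point to the margin itself as the quantity whose course matters. The one analysis over time points to how far the margin departs from what the surgeon expected. That measures how well surgeons predict their margins. It is useful, but it is a different question.

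Surgeons see the CT result in every case and later the CT-versus-pathology comparison, so their expectations may well shift during the study. A significant trend in the difference could then be reported as feedback changing margins when only expectations moved. A flat trend could be reported as no effect when margins and expectations rose together. Both errors would fall on a primary outcome.

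**Working it through.** **1. What the difference can show.** Define the gap as expected minus actual margin. Then trend(gap) = trend(expected) - trend(actual). Illustrative changes from first to last case:

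| Actual margin | Expectation | Gap |
|---|---|---|
| 0 mm | -5 mm | -5 - 0 = -5 mm |
| +5 mm | 0 mm | 0 - 5 = -5 mm |
| +5 mm | +5 mm | 5 - 5 = 0 mm |

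The gap trend cannot separate the first two rows, and it misses the third. It does respond when margins rise and expectations do not.

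**2. Simulation.** Inputs from the protocol: 80 cases, two-sided 0.05, and SD 8.52 (CT margin in the previous clinical study; no unit is printed, read as mm). Assumptions: equal SD for expectation and margin, correlation 0.5, shifts of 10 mm over the whole course, equally spaced cases, no surgeon effect, 4,000 trials per scenario.

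| Scenario | Gap trend significant | Margin trend significant |
|---|---|---|
| Margin flat, expectation -10 mm | 86% | 5% |
| Both +10 mm | 5% | 86% |
| Margin +10 mm, expectation flat | 86% | 87% |
| No change | 5% | 5% |

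The two targets agree in the last two scenarios and give opposite answers in the first two.

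**3. Precision of the margin trend.** The protocol attaches no SD, effect size or power to its 80 cases, so it has no figure to reproduce. Assumptions: SD 8.52 mm (segmentectomy and wedge mixed), fixed surgeon intercepts, no covariates, no random slope. Eight surgeons is also an assumption; of including all nine, the protocol says "As this is unlikely as not all surgeons will perform wedge resections".

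For a surgeon with n cases, the sum of squares of case order is n(n² - 1)/12. The SE per case step is SD/√(total sum of squares). Degrees of freedom are 80 - 8 - 1 = 71, so t = 1.994.

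*Balanced, 8 × 10 cases:*
- Sum of squares: 8 × 10 × 99/12 = 660.
- SE per step: 8.52/√660 = 0.332 mm; over the 9 steps from case 1 to case 10, 2.98 mm.
- 95% CI half-width: 1.994 × 2.98 = 5.95 mm.
- By noncentral t, 80% power at 8.48 mm (8.48/11.74 = 72% of the previous study's mean CT margin) and 38% power for 5 mm.

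*Uneven, assumed 25-18-13-9-6-4-3-2 cases, common per-case slope:*
- Sum of squares: 1300 + 484.5 + 182 + 60 + 17.5 + 5 + 2 + 0.5 = 2051.5.
- SE per step: 8.52/√2051.5 = 0.188 mm.
- Over 9 steps: half-width 3.38 mm, 80% power at 4.81 mm.
- Over 24 steps: half-width 9.00 mm, 80% power at 12.82 mm.

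*Study-wide case order scaled 0 to 1, balanced surgeons' cases spread at random (mean sum of squares 6.23):* SE 8.52/√6.23 = 3.41 mm, half-width 6.81 mm, 80% power at about 9.7 mm.

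A change in mm therefore means little unless its time scale and span are stated.

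**The case against.** The strongest reply is that the Statistics sentence is loosely worded. A difference of process between two margins over the course may mean comparing two trajectories, that is, a model with margin type, time and their interaction. That model contains the actual-margin slope, and which coefficient is reported is often left to a SAP. This stands in part: a reader might infer that the trial cannot estimate the margin trend, and the documents do not support that. But on this reading too the stated target is the difference, and no sentence names the margin slope as the result for outcome 2. The issue is a target that differs from the protocol's own outcome, not omitted detail.

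Second, the pairing is deliberate. Questionnaire 2 is collected to assess the contribution of feedback, and a case-specific expectation may act as a reference for case difficulty. That is a good reason to keep the analysis, but it does not make prediction accuracy the same as margin length. A reader might also infer that the gap is blind to margin change. It is not; it is ambiguous.

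Third, Statistics does not assign analyses to outcomes, and a team holding both quantities can see which one moved. So misreporting is a risk, not something the protocol commits to.

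Fourth, the margin trend has its own weakness: case mix or secular change could produce it. This stands in full, and the fix has to say so.

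**Conclusion.** The mismatch holds and should be fixed. The outcome is the course of the margin; the stated target over time is the course of the expected-versus-actual difference. By algebra alone the two can disagree in either direction, and this does not depend on the simulated or assumed figures.

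Two further inferences are not supported. Naming the margin trend would not show that feedback caused it, since the protocol describes no comparison group or feedback-free period. Nor does an uneven spread of cases across surgeons necessarily worsen precision: over the same 9 steps the assumed uneven spread gives a half-width of 3.4 mm against 5.95 mm for the balanced one, and the 9.0 mm figure arises only from extending the span to 24 steps.

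The precision figures rest on the previous study's total SD, which mixes two procedures. Covariates and within-surgeon comparison would tend to reduce it. Confidence is medium, because the wording of the mixed-model sentence admits more than one reading.

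**What to change.** In Statistics:
- Name the trend in the actual margin, over case order or calendar time, as the result for primary outcome 2.
- Define the actual margin as the intraoperative CT margin of the first wedge specimen, measured as Study Plan and Methods describes.
- Estimate the trend with a linear mixed model that has a surgeon random effect, and tumor size and tumor-to-pleura distance as covariates. Report it in mm with a 95% CI, and state the time scale and span.
- Keep the expected-versus-actual model and the Bland-Altman analysis as supporting calibration analyses.
- State that the trend describes change over the course and cannot by itself be attributed to feedback, and that a non-significant trend is not evidence of no effect.

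The cost is a few sentences and one more model in R. CT margin, surgery date, surgeon number and both covariates are already in the data list. If the team prefers the margin after additional resection as the actual margin, it should say so before analysis. The data list names no re-measured CT margin, so that choice may need one more data item. The remaining downside is limited precision: about 6 mm either side over a surgeon's 10 cases under the balanced assumption.

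### CT margin is compared with pathological margin only by Pearson correlation and an ROC curve, so no stated analysis gives the bias or scatter in mm of the length surgeons act on

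*Protocol*

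**What the plan says.** The Statistics section of the protocol assigns a method to each pair of measurements:

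- **CT against pathology:** Pearson's "correlation analysis will be performed to analyze the correlation between the parameters measured on CT and on pathological analysis". In addition, "ROC curves will be used to assess the CT margin to predict short pathological margin".
- **Expectation against actual margin:** a linear mixed model over the course of the study, and "Limits of agreement analysis will be performed per the Bland-Altman method to evaluate agreement between preoperative expectation for surgical margin and actual margin".

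Study Plan and Methods describes how the CT length is used in theatre: "Surgeons will wait and refer to these results, and make a decision if additional resection should be made". It also says that, once each patient's pathology is known, "surgeons will receive the results of the margin length comparison (CT based margin and pathological margin"). No statistic is named for that comparison. Outcome Measures makes the validity of the feedback's contribution to the treatment decision part of the primary outcome.

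The section on the pre-clinical study treats pathology as the gold standard for margin length. The results of the previous clinical study report that "Surgical margin measured by CT was significantly longer than pathological margin", that "21% surgical margin length reduction was observed from CT to pathological assessment", and conclude: "Surgeons should be aware that CT assessed surgical margin will be longer than pathological margin".

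**The concern.** The question for a surgeon reading a CT margin is how many mm it is likely to differ from the pathological margin, on average and in the single case. Pearson's r measures linear association, and the AUC measures how well CT ranks specimens. Both can be high when CT reads consistently and substantially long.

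Bland-Altman analysis is the method that answers the question, and the protocol already uses it, but for another pair. The protocol does not define the actual margin as CT or pathological. Under either reading the other member of the pair is the preoperative expectation, so the analysis is never CT minus pathology.

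The trial could therefore finish with a correlation and an AUC while leaving unquantified the very discrepancy the protocol warns surgeons about.

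**Working it through.** **Inputs** (protocol, previous clinical study, Results): CT margin 11.74 ± 8.52; pathological margin 10.08 ± 7.22; r = 0.7679; p = 0.033; 52 specimens from 50 patients. The unit is not printed and is taken as mm; the ± values are taken as SDs; the 52 specimens are treated as independent.

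**1. Reproducing the stated p-value.**
- SD of differences = √(8.52² + 7.22² − 2 × 0.7679 × 8.52 × 7.22) = 5.50.
- Mean difference = 11.74 − 10.08 = 1.66.
- Paired t = 1.66 / (5.50/√52) = 2.18, p = 0.034, against the stated 0.033.
- An unpaired test gives p = 0.29. The figures fit a paired analysis, which supports the derived SD.

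**2. Agreement implied by those figures.**
- Bias 1.66 mm; 95% CI 1.66 ± 2.008 × 5.50/√52 = 0.13 to 3.19 mm.
- 95% limits of agreement 1.66 ± 1.96 × 5.50 = −9.1 to +12.4 mm, if differences are normal with constant spread.

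**3. What r and the AUC cannot see.** In 400,000 simulated bivariate normal pairs with these means, SDs and r (short pathological margin taken as under 10 mm, an assumption):

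| Change to CT | r | AUC | Bias (mm) | Limits (mm) |
|---|---|---|---|---|
| none | 0.768 | 0.865 | 1.7 | −9.1 to +12.4 |
| add 5 mm | 0.768 | 0.865 | 6.7 | −4.1 to +17.4 |
| multiply by 1.5 | 0.768 | 0.865 | 7.5 | −9.2 to +24.3 |

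**4. Sensitivity to shape.** A pathological margin cannot be negative, so the upper limit of 12.4 mm cannot apply to a CT reading shorter than that. The table gives the central 95% of differences for skewed margins with the same means, SDs and r. The 15 mm split uses the figure cited in Study Background, for scale only.

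| Shape | All readings (mm) | CT under 15 mm (mm) |
|---|---|---|
| Lognormal | −8.0 to +14.2 | −7.1 to +6.5 |
| Gamma, Gaussian copula | −8.5 to +14.3 | −8.4 to +7.3 |

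A constant band is too wide for short readings, but scatter of several mm remains.

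**5. Does the difference change with length?**
- Slope of difference on mean = [(8.52² − 7.22²)/2] / [(8.52² + 7.22² + 2 × 0.7679 × 8.52 × 7.22)/4] = 0.187.
- The corresponding correlation is 0.251; t = 1.84 on 50 df, p = 0.072. A change with length is possible but not shown.
- The means give a reduction of 1.66/11.74 = 14.1%, against the stated 21%. The basis of the 21% is not given; it may be an average of per-specimen percentages. Whether mm or a proportion is the better scale needs checking.

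**6. A second source in the protocol.** The pig-lung experiment reports CT longer by 3.50 ± 2.69 mm (n = 30). If 2.69 is an SD, the limits are 3.50 ± 1.96 × 2.69 = −1.8 to +8.8 mm.

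**7. Precision available in this trial**, with SD 5.50 mm:
- Half-width for the bias = t × 5.50/√n.
- Half-width for each limit = t × 5.50 × √(1/n + 1.96²/(2(n − 1))).
- With 80 pairs: 1.2 and 2.1 mm.
- With 74 pairs, 80 × (1 − 0.074), at the previous study's 7.4% unreadable rate: 1.3 and 2.2 mm.

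**The case against.** The protocol says that Pearson's method will assess correlation, which is true; it does not call r a measure of agreement. CT-pathology agreement is not a named aim, and the measurement question was largely the business of the previous study. For a decision on additional resection, the ROC curve is a fitting tool, and a cut-off read from it would absorb a constant offset. If means, SDs and r are reported, a reader can rebuild the bias and limits as above. The paired data are collected, so nothing is lost for good.

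Much of this is fair and bears on weight: this is a cheap improvement, and no primary conclusion is shown to change. It does not remove the point. An ROC cut-off reports neither the offset nor the scatter. Rebuilding from summary statistics yields only a constant band, and cannot show whether bias or spread changes with length. Nor is this detail left to an analysis plan: the protocol itself fixes the methods for this pair.

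Three caveats on the numbers stand:

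- The CT-pathology difference mixes CT error, measurement error at pathology and tissue shrinkage, which the protocol names as a possible cause. It is not CT error alone, but it is the difference surgeons are warned about.
- The pig-lung limits are about half as wide as those from patients, although pseudo-nodules in pig lung are a weaker proxy.
- The previous study mixed segmentectomy and wedge resection, whereas this trial enrols wedge resections only, so an SD of 5.50 mm may not carry over exactly.

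**Conclusion.** The concern holds. No analysis stated in the protocol estimates the mean difference or the scatter, in mm, between CT and pathological margin, and the method that would do so is assigned to another pair. A plausible spread is the previous study's SD of differences of about 5.5 mm, with limits of roughly −9 to +12 mm, narrower for short readings and narrower in pig lung. Those figures rest on the assumptions stated in the working; the gap in the plan does not depend on them. The change should be made, since the feedback's validity is part of the primary outcome and the CT length is what is fed back.

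**What to change.** Add to Statistics, in words such as these:

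> Bland-Altman analysis will also be performed for CT margin minus pathological margin of the same initially resected specimen. Bias and 95% limits of agreement will be reported with 95% confidence intervals. The difference will be regressed on the mean of the two; if bias or spread changes with margin length, regression-based or log-ratio limits will be reported.

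Where a margin of 0 mm occurs, the log-ratio is undefined and the regression-based form should be used. Keep Pearson's r as descriptive and the ROC curve for classification. When the expected precision is described, give the pig-lung spread beside the patient figures and note the previous study's mix of procedures.

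The cost is three sentences, one plot and one table. Both margins are already listed in Data Collection and Monitoring, so no patients, procedures or data items are added. The one drawback for the investigators is that reported accuracy will look less favourable than r alone.

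### The Bland-Altman analysis of expected versus actual margin has no provision for clustering by surgeon; if surgeons differ systematically, intervals computed as for independent pairs would be too narrow

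*Protocol*

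**What the plan says.** The protocol's Statistics section plans two analyses of the gap between expected and actual margin. The first is a mixed model for its development: "A linear mixed model will be performed to analyze the difference of the process between expected and actual margin over the course". The second is an agreement analysis: "Limits of agreement analysis will be performed per the Bland-Altman method to evaluate agreement between preoperative expectation for surgical margin and actual margin". The software sentence names GraphPad Prism for the work in general and ties R to one task: "R (for linear mixed model) will be used for statistical analysis". Neither the random effects of the mixed model nor any surgeon term for the agreement analysis is stated.

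The Sample size section sets the total: "We aim to evaluate 80 cases over 2 years". On surgeons it says "We would like to include all 9 thoracic surgeons in our division", then "As this is unlikely as not all surgeons will perform wedge resections", and concludes that "we will enroll consecutive patients regardless of who the attending surgeon is". Study Plan and Methods describes what is asked of the surgeon case by case: "At each surgery, we ask for questionnaire 2 orally before and after resection to assess the contribution of feedback to margin results". The questionnaire items are not shown, but this is the evident source of the expected margin. Data Collection and Monitoring lists the attending surgeon's study number among the recorded items.

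**The concern.** In this comparison the surgeon is in effect the measuring instrument. One side of each pair is a surgeon's own estimate, and the same few surgeons supply it repeatedly. A surgeon who habitually over- or underestimates shifts all of his or her differences in the same direction, so those differences are correlated. The ordinary Bland-Altman calculation assumes independent pairs.

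Enrolment is consecutive and caseloads are neither balanced nor capped, so the busiest surgeons may largely determine the mean difference. An interval computed from 80 independent pairs would then overstate how much is known about surgeons' expectation in general. The spread between surgeons, which is of interest in itself, would also be merged into a single SD.

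This is separate from change over time. It concerns correlation between cases of the same surgeon, which exists even if nobody's expectation changes during the study.

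**Working it through.** **The plan's own figure.** The 80 cannot be reproduced. The protocol gives no SD, precision target, power or ICC for it.

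**Inputs.** From the Sample size section: N = 80 cases and at most nine surgeons. Assumed, because the protocol gives neither: ICC of the differences within surgeon from 0 to 0.30, and two caseload splits of 80.

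- Near-equal, eight surgeons with 9 cases and one with 8: Σn²/N = (8 × 81 + 64)/80 = 712/80 = 8.9.
- Skewed, 24/18/13/9/6/4/3/2/1: Σn²/N = 1216/80 = 15.2.

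**Formulas.**

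- Design effect: DE = 1 + ICC × (Σn²/N − 1).
- Effective n = 80/DE.
- Approximate coverage of a nominal 95% interval for bias = 2Φ(1.96/√DE) − 1.

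Example: near-equal caseloads at ICC 0.30 give DE = 1 + 0.30 × 7.9 = 3.37, and the skewed split gives 1 + 0.30 × 14.2 = 5.26.

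| ICC (assumed) | Near-equal: DE / effective n / coverage | Skewed: DE / effective n / coverage |
|---|---|---|
| 0 | 1.00 / 80 / 95% | 1.00 / 80 / 95% |
| 0.05 | 1.40 / 57 / 90% | 1.71 / 47 / 87% |
| 0.10 | 1.79 / 45 / 86% | 2.42 / 33 / 79% |
| 0.20 | 2.58 / 31 / 78% | 3.84 / 21 / 68% |
| 0.30 | 3.37 / 24 / 71% | 5.26 / 15 / 61% |

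**Check by simulation (40,000 runs each).** At ICC 0.05, 0.10 and 0.20, coverage was 90%, 86% and 78% with near-equal caseloads. It was 87%, 79% and 68% with a very similar skewed split (24/18/12/9/6/5/3/2/1). With five surgeons of 16 cases each it was 86%, 78% and 66%. At ICC 0 it was 95% throughout.

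**Interval width.** For ICC 0.05 to 0.30 the standard error grows by √1.40 = 1.2 up to √5.26 = 2.3. With nine surgeons, using t on 8 rather than 79 degrees of freedom adds a further 2.306/1.990 = 1.16.

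**Scale in millimetres, for illustration only.** The protocol has no SD for expected minus actual margin. The earlier clinical study's CT and pathology margins (SDs 8.52 and 7.22, r = 0.7679) give an SD of differences of √(8.52² + 7.22² − 2 × 0.7679 × 8.52 × 7.22) = 5.50. If that SD applied:

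- independent pairs: half-width 1.990 × 5.50/√80 = 1.2 mm;
- near-equal, ICC 0.10: 1.2 × √1.79 = 1.6 mm, or 1.9 mm on 8 degrees of freedom;
- skewed, ICC 0.20: 1.2 × √3.84 = 2.4 mm, or 2.8 mm on 8 degrees of freedom.

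**The limits themselves.** The expected pooled variance is the total variance times 1 − ICC × (Σn²/N − 1)/(N − 1).

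- Near-equal, ICC 0.05: 1 − 0.05 × 7.9/79 = 0.995, so the SD is low by about 0.3%.
- Skewed, ICC 0.20: 1 − 0.20 × 14.2/79 = 0.964, so the SD is low by about 2%.

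**The case against.** A reader might infer that the protocol treats the 80 differences as independent and that its interval for bias is therefore wrong. The text does not go that far. It does not state independence and it announces no interval for the bias, so no stated interval can be faulted. Ordinary Bland-Altman is an inference from the named method, the absence of a surgeon term and the software sentence. A SAP that is not shown could specify a clustered version. The mixed model of the same difference may also already include surgeon, since its random effects are not given.

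The target matters too. This is a single-centre study that would like to include every surgeon in the division, and it states no aim to generalise to others. If the bias is meant only for these surgeons at their own caseloads, the spread between them is not sampling error. The simple interval is then not too narrow, and the greater weight of busy surgeons is what a case average should give.

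Finally, the output the protocol actually names, the limits of agreement, barely changes. Every ICC and caseload split above is assumed, and the lowest coverage pairs the highest ICC with a skewed split.

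All of this stands and makes the point conditional. It does not remove it. The only version of the analysis to which the wording points has no protection against clustering, although the surgeon number needed for it is recorded.

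**Conclusion.** The point holds in conditional form. The protocol names an agreement analysis without provision for differences clustered within at most nine surgeons. If surgeons differ systematically, and if the conclusion is meant to reach beyond their own cases, an interval for bias computed as for independent pairs would be too narrow. The size ranges from nothing at ICC 0 to a standard error understated by a factor of about 1.8 (√3.37, near-equal) or 2.3 (√5.26, skewed) at ICC 0.30. Intervals for the limits would be affected in the same direction, but this was not quantified.

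It would be wrong to read this as saying that the limits of agreement are materially biased: the pooled SD is low by only about 0.3% to 2% for ICC 0.05 to 0.20. Outcome Measures does not list agreement as an outcome, and the primary question of change over the course is addressed by the mixed model. The priority is therefore minor.

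**What to change.** Add a sentence to the Statistics section: bias and limits of agreement will be estimated in R from a model of the expected-minus-actual difference with a random surgeon effect, using the attending surgeon's study number.

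- Bias is the fixed intercept, with its interval on surgeon-level degrees of freedom.
- Limits are bias ± 1.96 × √(between-surgeon variance + within-surgeon variance), with intervals that also allow for the small number of surgeons.
- Both variance components are reported, with the number of cases per surgeon.
- A patient term is added if any patient contributes more than one specimen; the earlier clinical study analysed 52 specimens from 50 patients.
- The text says whether the bias is meant for these surgeons only or for surgeons more widely.

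The cost is a little more analysis in software already planned and a wider interval. With nine surgeons or fewer, the between-surgeon variance will itself be estimated imprecisely, and the report should say so. No new data are needed.
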